C _{min}	minimum observed concentration over the dose interval
CNS	central nervous system
CR	complete response
CT	computed tomography
CTCAE	Common Terminology Criteria for Adverse Events
CYP	cytochrome P450
DAT	direct antiglobulin test
DNA	deoxyribonucleic acid
ECOG	Eastern Cooperative Oncology Group
EDC	electronic data capture
EOT	end of treatment
ECG	electrocardiogram
eCRF	electronic case report form
FACIT	Functional Assessment of Chronic Illness Therapy
FAS	full analysis set
Fc	fragment crystallizable

Abbreviation	Definition
FDA	Food and Drug Administration
FSH	follicle-stimulating hormone
GCP	Good Clinical Practice
HBV	hepatitis B virus
HCV	hepatitis C virus
HIPAA	Health Insurance Portability and Accountability Act of 1996
HIV	human immunodeficiency virus
IC ₅₀	concentration that results in 50% inhibition
IC ₉₀	concentration that results in 90% inhibition
ICF	informed consent form
ICH	International Conference on Harmonisation
IEC	independent ethics committee
IgG	immunoglobulin G
IgM	immunoglobulin M
IL	interleukin
IN	Investigator Notification
IRB	institutional review board
IRT	interactive response technology
LDH	lactate dehydrogenase
MedDRA	Medical Dictionary for Regulatory Activities
MRI	magnetic resonance imaging
NCI	National Cancer Institute
NK	natural killer
PD	pharmacodynamic
PD-1	programmed cell death protein 1
ΡΙ3Κδ	phosphatidylinositol 3-kinase enzymes delta isoform
PIP2	phosphatidylinositol-4,5-bisphosphate
PIP3	phosphatidylinositol-3,4,5 trisphosphate
PJP	Pneumocystis jiroveci pneumonia
PK	pharmacokinetic
PML	progressive multifocal leukoencephalopathy

Abbreviation	Definition
PR	partial response
RBC	red blood cell
RNA	ribonucleic acid
SAE	serious adverse event
TEAE	treatment-emergent adverse event
t _{max}	time to maximum concentration
Treg	regulatory T cell
ULN	upper limit of normal
wAIHA	warm-type autoimmune hemolytic anemia
WBC	white blood cell

1. PROTOCOL SUMMARY

Protocol Title: A Phase 2, Open-Label Study of INCB050465 in Participants With

Autoimmune Hemolytic Anemia

Protocol Number: INCB 50465-206

Objectives and Endpoints:

Objectives	Endpoints
Primary	
To evaluate the efficacy of INCB050465 in the treatment of participants with AIHA.	• Proportion of participants attaining a CR (defined as hemoglobin > 12 g/dL not attributed to transfusion effect* and the normalization of hemolytic markers) at any visit from Week 6 to Week 12.
	• Proportion of participants attaining a PR (defined as hemoglobin 10-12 g/dL or ≥ 2 g/dL increase from baseline not attributed to transfusion effect and the normalization of hemolytic markers) at any visit from Week 6 to Week 12.
	*No transfusion effect definition: >1 week since last transfusion.
To evaluate the safety of INCB050465 administered as repeat doses in participants with AIHA.	Safety and tolerability will be assessed by monitoring AEs, measuring vital signs and ECGs, and conducting clinical laboratory blood and urine sample assessments.

Overall Design:

Study Phase	Phase 2
Clinical Indication	AIHA
Population	Men and women, aged 18 years or older with primary AIHA without evidence of a lymphoproliferative malignancy.
Number of Participants	Approximately 25
Study Design	Open-label, multicenter study
Estimated Duration of Study	Treatment duration will vary among participants. The initial study period will be 28 weeks in duration. For participants who are eligible for an extension of treatment based on their clinical response, the treatment duration may be extended with sponsor approval.
Safety Review Committee	Yes (internal)

Treatment Groups and Duration:

Participation is 28 weeks for participants who are not eligible for an extension based on clinical response and includes the following:

• Screening: up to 28 days

• Treatment: up to 12 weeks

- Extension period: For participants receiving benefit from study drug, further participation may continue with sponsor approval until the drug is available through another clinical study, or is commercially available, or the sponsor stops the study or the study drug development.
- Follow-up: up to 12 weeks (3 months)

Cohort 1: INCB050465 1 mg QD for up to 12 weeks. At Week 6, participants who fulfill dose increase criteria (see definition below) will be offered INCB050465 2.5 mg QD for up to 6 weeks. If there are any tolerability issues in individual participants who received 2.5 mg, the dose may be decreased to 1 mg.

[figure not shown]
Cohort 2: INCB050465 2.5 mg QD for up to 12 weeks. If there are any tolerability issues in individual participants, the dose may be decreased to 1 mg.

Criteria for dose increase: (1) Continue to require transfusions by Week 6 visit, or (2) do not attain a meaningful clinical response (at least a stabilization ≥ 2 g/dL increase in hemoglobin from baseline to Week 6). Dose increases require sponsor preapproval (see Section 6.6).

Participants who complete the 12-week treatment period and continue to receive clinical benefit from study drug may enter into an extension period with sponsor approval to continue receiving INCB050465 until the drug is available through another clinical study, or is commercially available, or the sponsor stops the study or the study drug development.

The study design is shown in Figure 1 below.

Figure 1: Study Design Schema

- ^a Cohort 1: N = 10; no more than 3 CAD or mixed-type AIHA participants.
- b Cohort 2: N = approximately 15, with approximately 5 CAD AIHA and up to 8 wAIHA participants; the remainder can be wAIHA, CAD, or mixed-type AIHA participants.

 Participants in Cohort 2 may begin enrollment after enrollment of a minimum of 6 wAIHA participants in Cohort 1 and review of safety and efficacy through Week 6.
- ^c (1) At Week 6, participants who receive 1 mg QD study drug and who fulfill dose increase criteria* may have their dose increased to 2.5 mg QD of INCB050465 until Week 12.
 - (2) If there are any tolerability issues in individual participants who received 2.5 mg, the dose may be decreased to 1 mg.
- d If there are any tolerability issues in individual participants who received 2.5 mg, the dose may be decreased to 1 mg.
- ^c If relapse of AIHA occurs within this period, PD and clinical laboratory markers of hemolysis will be assessed, and the participants will be treated based on investigators' decision.
- * Criteria for dose increase in individual participants in Cohort 1 (see Section 6.6):
- (1) Continue to require transfusions by Week 6 visit, or
- (2) Do not attain a meaningful clinical response (at least a stabilization ≥ 2 g/dL increase in hemoglobin from baseline to Week 6).

Table 1: Schedule of Assessments

		Screening				Trea	tment					Follow-Up ^a	ı
Procedure	Protocol Section		Day 1	Wk 1 ± 3 days	Wk 2 ± 3 days	Wk 4 ± 3 days	Wk 6 ^b ± 3 days	Wk 8 ± 3 days	Wk 10 ± 3 days	Wk 12 ± 3 days (EOT)	Month 1 + 5 days	Month 2 ± 5 days	Month 3 ± 5 days (EOS)
Administrative procedures													
Informed consent	8.1.1	X											
Contact IRT	8.1.3	X	X	X	X	X	X	X	X	X	X	X	X
Review inclusion and exclusion criteria	5.1, 5.2	X	X										
Demography and medical history	8.1.4	X											
Prior/concomitant medications	8.1.5	X	X	X	X	X	X	X	X	X	X	X	X
Study drug accountability and assess compliance	6.5			X	X	X	X	X	X	X			
Study drug dispensing	6.1		X			X		X					
Prophylactic treatment for PJP	6.7.1.1		X	X	X	X	X	X	X	X	X	X	X
Safety procedures/assessments													
Physical examination ^c	8.3.2	Xc	X ^{c,d}	X	X	X		X		X			Xc
Vital signs ^e	8.3.3	X	X	X	X	X	X	X	X	X			X
Serology ^f	8.3.5.7	X											
D-Dimer	8.3.5.5	X				X		X		X			
Vitamin B12/folic acid	8.3.5.2	X											
FSHg	8.3.5.6	X											
Serum pregnancyh	8.3.5.6	X											
Urine pregnancy ^h	8.3.5.6		X	X	X	X	X	X	X	X			
Urinalysis	8.3.5.4	X								X			
Serum chemistries ⁱ	8.3.5.1 8.3.5.3	X	X	X	X	X	X	X	X	X	X	X	X
12-Lead ECG ^j	8.3.4	X			X			X		X			
AE assessment	8.3.1	X	X	X	X	X	X	X	X	X	X	X	X

Table 1: Schedule of Assessments (Continued)

		Screening	Treatment							Follow-Up ^a			
Procedure	Protocol Section	Days -28 to -1	Day 1	Wk 1 ± 3 days	Wk 2 ± 3 days	Wk 4 ± 3 days	Wk 6 ^b ± 3 days	Wk 8 ± 3 days	Wk 10 ± 3 days	Wk 12 ± 3 days (EOT)	Month 1 + 5 days	Month 2 ± 5 days	Month 3 ± 5 days (EOS)
Efficacy assessments													
Hematology	8.2.1	X	X	X	X	X	X	X	X	X	X	X	X
Hemolysis markers ^k	8.2.1	X	X	X	X	X	X	X	X	X	Xk	X^k	Xk
DAT and cold agglutinin levels	8.2.2	X								X			
Complement assessment (CH50, C3, and C4)	8.2.1		X							X			
FACIT-Fatigue sub-scale	8.2.3		X				X			X	X	X	X
PK plasma sampling ^l	8.4			X	Xm			Xm		X			

^m No food intake 4 hours predose and 1 hour postdose on Weeks 2 and 8.

VV-CLIN-000602 CONFIDENTIAL

^a For participants who are not eligible to enter into the extension period.

^b Dose modification.

^c Comprehensive physical examination at screening, Day 1, and EOS; targeted physical examination at all other time points.

^d Height and body weight will only be assessed at Day 1.

^e Vital signs will include body temperature, respiratory rate, blood pressure, and pulse.

f Serology includes HIV, hepatitis, anti-Streptolysin antibody, and anti-phospholipid antibody tests.

g For women of nonchildbearing potential only (ie, surgically sterile with a hysterectomy and/or bilateral oophorectomy OR postmenopausal, defined by last menstrual period > 12 months before screening and confirmed by FSH).

^h For women of childbearing potential only.

¹ Ferritin, iron, and total iron-binding capacity will be tested at screening for all participants and at Week 6 if the participant has ongoing transfusions requirements during the study.

Single ECG. At screening, in the event that a single QTcF is > 470 milliseconds for males or > 480 milliseconds for females, triplicate ECG measurements may be performed.

k Hemoglobin, haptoglobin, LDH, reticulocyte count, total bilirubin and direct/indirect bilirubin are hemolytic markers will be measured. During follow-up, these hemolytic markers should be assessed if a participant becomes symptomatic or starts new treatment; relevant biomarkers should also be included.

Plasma for PK analysis will be collected predose and 1, 2, and 4 hours postdose at Weeks 2 and 8. Predose PK will be collected at Weeks 1 and 12.

Table 2: Schedule of Assessments for the Extension Period

		Extension Period			Follow-Up	
Procedure	Protocol Section	At Least Every 8-12 Weeks in Clinic	EOT Extension Period	Month 1 + 5 days	Month 2 ± 5 days	Month 3 ± 5 days (EOS)
Prior/concomitant medications	8.1.5	X	X	X	X	X
Study drug dispensing	6.1	X				
Study drug accountability and assess compliance	6.5	X	X			
AE assessment	8.3.1	X	X	X	X	X
Prophylactic treatment for PJP	6.7.1.1	X	X	X	X	X
Hematology ^{a,b}	8.2.1	X	X	X	X	X
Hemolysis markers ^a	8.2.1	X	X	X	X	X
Serum chemistries ^a	8.3.5.1	X				

^a Performed at each site as per the standard of care for participant's condition and monitoring at the investigator's discretion. Frequency to be determined by the investigator if it is necessary to monitor any other ongoing clinical condition.

^b Hematology panel will be performed at local laboratory.

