4. STUDY DESIGN

4.1. Overall Design

This is a multicenter, open-label study designed to evaluate the safety and efficacy of INCB050465 administered orally to participants with AIHA who have decreased hemoglobin and evidence of ongoing hemolysis that requires treatment intervention. Participants with primary warm, cold (CAD), and mixed-type AIHA without an underlying lymphoproliferative malignancy or autoimmune related hemolytic anemia and have failed at least 1 prior treatment for AIHA will be eligible for enrollment. Participants will be treated for 12 weeks. There are 2 cohorts in this study: Cohort 1, with up to 10 participants, with no more than 3 cold (CAD)/mixed-type AIHA participants to appropriately reflect response in the overall population, which is predominantly warm AIHA; and Cohort 2, with approximately 15 participants, with approximately 5 CAD AIHA, up to 8 warm AIHA, and the remainder from any of the 3 AIHA types. Cohort 2 distribution and increased number of participants are intended to better evaluate CAD AIHA patients and possible signal observed in Cohort 1, as well as account for higher baseline variability seen in the wAIHA subpopulation. The first cohort (Cohort 1, n = 10participants) enrolled will initially receive INCB050465 1 mg QD. At Week 6, participants who continue to require transfusions or do not attain a meaningful clinical response (at least a stabilization ≥ 2 g/dL increase in hemoglobin from baseline to Week 6) may have their dose increased, with sponsor preapproval, to 2.5 mg QD of INCB050465 until Week 12 (see Section 6.6). If there are any tolerability issues in individual participants who received 2.5 mg, the dose may be decreased to 1 mg. Following enrollment of a minimum of 6 warm AIHA participants in the first cohort and review of safety and efficacy through Week 6, Cohort 2 may begin enrollment. Participants in Cohort 2 (n \approx 15) will receive INCB050465 2.5 mg QD for 12 weeks. If there are any tolerability issues, the dose may be decreased to 1 mg. The investigator and sponsor should review and agree any dose increases or decreases. Following the last dose of INCB050465, participants will be eligible for a 12-week (3 months) follow-up for evaluation of the safety and durability of response.

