8.3.5.7. Serology

Anti-Streptolysin antibody, anti-phospholipid antibody, hepatitis, and HIV tests will be performed at a central laboratory (see Table 1). Hepatitis and HIV tests will be conducted during the screening period. If participants are positive for active disease, they should not be enrolled per exclusion criteria. Note: HIV screening test is optional for participants enrolled in the United States, but participants with known HIV infection enrolled in the United States will be excluded.

Table 5: Required Laboratory Analytes

Serum Chemistries	Hematology ^{a,b}	Urinalysis With Microscopic Examination	Screening Serology	Coagulation	
Albumin	CBC, including:	Color and appearance	Hepatitis B surface antigen	D-Dimer	
Alkaline phosphatase	Hemoglobin	pH and specific gravity	Hepatitis B surface antibody		
ALT	Hematocrit	Bilirubin	Hepatitis B core antibody		
AST	Platelet count	Glucose	Hepatitis C virus antibody		
Bicarbonate	RBC count	Ketones	Hepatitis C virus-RNA (only		
Blood urea nitrogen	WBC count	Leukocytes	performed if antibody positive)		
Calcium	De teum	Nitrite	HIV antibody		
Chloride	Differential count, including:	Occult blood	Anti-streptolysin antibody		
Creatinine	Basophils	Protein	Anti-phospholipid antibody		
Ferritin (screening visit and repeat at	Eosinophils	Urobilinogen			
Week 6 if participant has ongoing	Lymphocytes		Hemolysis Markers ^b		
transfusion requirements)	Monocytes	Haptoglobin (will be measured in	serum chemistry panel)		
Folic acid (screening visit)	Neutrophils	LDH (will be measured in serum chemistry panel)			
Glucose	Neutropinis	Reticulocyte count (will be measured in hematology panel)			
Haptoglobin	Absolute values must be	Hemoglobin (will be measured in hematology panel)			
Iron (screening visit and repeat at	provided for WBC differential				
Week 6 if participant has ongoing transfusion requirements)	laboratory results:	Total bilirubin ^c (will be measured	DAT and Cold Agglutinin Test		
LDH	Lymphocytes	DAT for IgG and C3d*			
Phosphate	Neutrophils	Cold agglutinin levels*			
Potassium		* Baseline and EOT			
Sodium		Other Assessments			
Total bilirubin ^c		Urinalysis			
Total protein		FSH			
Total iron-binding capacity		Urine pregnancy test (at site)			
(screening visit and repeat at Week 6		Serum pregnancy test			
if participant has ongoing transfusion	Complement assessment (CH50, C3, and C4)*				
requirements)		* Baseline and EOT			
Uric acid		Vitamin B12 (screening visit)			

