8.9.2. Additional Follow-Up Period

Participants will have additional follow-up assessments for 12 weeks (3 months) after EOT. Safety follow-up is included in this 12-week (3 months) additional follow-up period. The following information will be collected:

- The start date of new AIHA therapy.
- Type of therapy.
- Marker for hemolysis.

If the participant withdraws consent for study drug but continues in the follow-up period of the study, the above information will also be collected.

The site will also use continuing participant records to supply data on subsequent treatment regimens and disease activities in the eCRF.

For participants who receive study drug in the extension period, the safety follow-up is included in the 12-week (3-month) additional follow-up period and should occur 30 to 35 days after the last dose of study drug.

9. ADVERSE EVENTS: DEFINITIONS AND PROCEDURES FOR RECORDING, EVALUATING, FOLLOW-UP, AND REPORTING

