5. STATISTICAL METHODOLOGY

5.1. General Methodology

Unless otherwise noted, SAS® software (SAS Institute Inc, Cary, NC; Version 9.1 or later) will be used for the generation of all tables, graphs, and statistical analyses. Descriptive summaries for continuous variables will include, but not be limited to, the number of observations, mean, standard deviation, median, minimum, and maximum, and both the actual value and change and/or percentage from baseline (if available) will be analyzed. Descriptive summaries for categorical variables will include the number and percentage of participants in each category. All by-visit analyses will include the follow-up period if the data are available.

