2.2 Secondary Efficacy		
2.2.1	Summary of Participants Attaining a Complete Response by Visit	FAS
2.2.2	Summary of Participants Attaining a Partial Response by Visit	FAS
2.2.3	Summary of Participants Attaining a ≥ 2 g/dL Increase in Hemoglobin From Baseline	FAS
2.2.4	Summary of Hemoglobin by Visit	FAS

Table No.	Title	Population
2.2.5	Summary of Participants Requiring Transfusions	FAS
2.2.6	Summary of Participants Achieving Normalization of Hemolytic Markers by Visit	FAS
2.2.7	Summary of Daily Usage of Prednisone by Visit	FAS
2.2.8	Summary of FACIT-F Subscale by Visit	FAS
Safety		

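### Table 1 footnote k makes follow-up hemolysis markers conditional on symptoms or new treatment, against the unconditional panel rows and Section 8.9.2, so Month 1-3 marker summaries could rest on a selected denominator.

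*Protocol*

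**What the plan says.** Protocol Section 4.1 gives the purpose of the period after treatment: "participants will be eligible for a 12-week (3 months) follow-up for evaluation of the safety and durability of response". In Table 1 the hemolysis-marker row is marked at all visits, but the three follow-up cells carry footnote k again. That footnote names hemoglobin, haptoglobin, LDH, reticulocyte count, total bilirubin and direct/indirect bilirubin as the markers, and then says: "During follow-up, these hemolytic markers should be assessed if a participant becomes symptomatic or starts new treatment".

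Elsewhere the protocol sets no such condition. Section 8.9.2 lists "Marker for hemolysis" among the information to be collected during the 12 weeks. The Hematology and Serum chemistries rows of Table 1 are marked at Months 1, 2 and 3 with no reference to symptoms. Table 5 assigns each marker to a panel, for example "LDH (will be measured in serum chemistry panel".

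The SAP uses the follow-up data. Section 5.1 says: "All by-visit analyses will include the follow-up period if the data are available". Appendix A plans Table 2.2.6, "Summary of Participants Achieving Normalization of Hemolytic Markers by Visit", on the full analysis set.

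**The concern.** If a laboratory value is obtained because a participant is unwell or has been retreated, whether it is missing depends on the outcome being described. A by-visit normalization percentage then has a denominator weighted towards participants who are doing badly, and a by-visit change from baseline has the same fault. SAP Section 4.1.4 in general does not impute missing values, and the SAP has no rule for values that are absent because the participant was well.

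Marker normalization has also gained weight in this plan. SAP Section 10.1 removed the hemolysis component from the primary response definitions. The secondary normalization endpoint is now the only responder-type endpoint that addresses hemolysis directly, alongside the pharmacodynamic change-from-baseline endpoint. Section 2.6 of the protocol describes a disease of remission and relapse, so readers will look at the follow-up rows.

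**Working it through.** No figure in the documents bears on this point, so the check is a cross-reading.

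**Step 1. Schedule.** Table 1 has 12 visit columns: screening, Day 1, seven on-treatment weeks and three follow-up months (1 + 1 + 7 + 3 = 12).

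- Hemolysis markers: "Hemolysis markers ^k 8.2.1 X X X X X X X X X Xk X^k Xk". There are nine plain marks and three that carry k.
- Hematology: "Hematology 8.2.1 X X X X X X X X X X X X". All twelve marks are unconditional.
- Serum chemistries: also twelve marks. The footnote on that row concerns only the iron tests.

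**Step 2. Which panel carries each marker in footnote k (Table 5).**

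| Marker | Source in Table 5 | Due from everyone at Months 1-3? |
|---|---|---|
| Hemoglobin | Hematology panel; listed in that column | Yes |
| Haptoglobin | Serum chemistry panel; listed in that column | Yes |
| LDH | Serum chemistry panel; listed in that column | Yes |
| Total bilirubin | Listed under serum chemistries | Yes |
| Direct/indirect bilirubin | Reflex test when total bilirubin exceeds the upper limit of normal (footnote c) | When the reflex applies, whatever the symptoms |
| Reticulocyte count | Hematology panel according to the hemolysis block, but not listed in the hematology column | Unclear |

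So 4 of the 6 markers are scheduled for everyone, 1 is a reflex test and 1 is uncertain (4 + 1 + 1 = 6).

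**Step 3. Why the reticulocyte count is exposed.** Sections 8.2.1 and 8.3.5 send the hematology panel to local laboratories and describe it as including the blood count and differential. The hematology column of Table 5 lists only components of those two. A local laboratory working from that column could omit reticulocytes unless they are requested separately, and footnote k tells the site when to request the markers.

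**Step 4. Other texts that bear on the reading.**

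- Section 8.9.2 has no symptom condition, which points to collection from everyone.
- A footnote to Figure 1 has markers assessed on relapse. This fits a trigger for extra work-up.
- Footnote b of Table 5 leaves hematology panels and hemolysis markers to standard of care and investigator discretion, which adds to the uncertainty.
- Table 2 schedules markers after the extension without a symptom trigger, but its footnote a also leaves them to standard of care and discretion. It is not an unconditional comparator.

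**Step 5. Which outputs are affected.** SAP Section 7.4 does not say whether normalization means each marker separately or all together. If all together, one selectively measured marker selects the denominator of the whole Month 1-3 row of Table 2.2.6. If each separately, only that marker's row is affected. Follow-up summaries of pharmacodynamic markers are affected in the same way for whichever marker is triggered. Direct antiglobulin test, cold agglutinins and complement are not scheduled in follow-up, so footnote k does not touch them. Response by visit (SAP Section 7.2) uses hemoglobin and transfusion only, and is unaffected where the Hematology row is followed.

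**The case against.** The best defence is that footnote k does no harm. It does not contain the word only. It can be read, with the Figure 1 footnote, as asking for extra assessment when something happens, on top of panels that are due anyway. AE assessment and the fatigue scale are also unconditional at Months 1-3. A reader might infer that biochemical recurrence before symptoms goes unlooked for, or that the Month 1-3 rows contain only relapsing participants. The documents do not support that: hemoglobin, haptoglobin, LDH and total bilirubin are due from everyone. This part of the defence stands.

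It is also fair that the stakes are limited. The primary window ends at Week 12, neither document has a durability or relapse endpoint, and all efficacy analyses are exploratory and descriptive.

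The defence does not remove the conflict. The superscript is repeated on exactly the three follow-up cells, so the restrictive reading is a natural one. Footnote k names hemoglobin among the conditional markers, directly against the Hematology row. A site can follow either text and believe it complies, and for the reticulocyte count the panel listing does not settle the matter.

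**Conclusion.** The passages are inconsistent and must be reconciled. The ambiguity touches all 3 of 3 follow-up visits in Table 1. By schedule it leaves four of the six markers intact and exposes chiefly the reticulocyte count. Sites that follow footnote k might also report other markers selectively, even though the panels are due.

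The consequence is conditional: the Month 1-3 rows of SAP Table 2.2.6 and the follow-up marker summaries could rest on a selected denominator, to an extent set by site practice. The documents do not say how many participants will be in this follow-up or how sites read the footnote, so a bias figure would be invention. Nor should untested participants be presumed not normalized: the SAP has no such rule, and the full analysis set is everyone treated, not everyone in follow-up.

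The reticulocyte point rests on the hematology column of Table 5 as it reads in the text, and should be confirmed on the laboratory requisition.

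A reader might also conclude that change after stopping drug becomes interpretable once the footnote is repaired. It does not. Table 1 follow-up is for participants not eligible for the extension, and those with clinical benefit may enter the extension instead. That selection is a separate limit, which this change does not remove.

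**What to change.** **Protocol.**

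- Delete the conditional sentence from footnote k, or restate it as a trigger for additional unscheduled testing only.
- List the reticulocyte count in the hematology column of Table 5, so that all markers are reported from the panels already scheduled at Months 1, 2 and 3.
- Bring footnote b of Table 5 and Section 8.9.2 into line with that reading.

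**SAP.**

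- State in Section 7.4 whether normalization is per marker or for all markers together.
- In Table 2.2.6 and the marker summaries, show the number of participants tested for each marker at each follow-up visit.
- For data already collected, give a normalization percentage only for markers measured irrespective of symptoms, and list the values of the rest. A workable check is to compare, at each visit, the number with a result for the marker against the number with any result from its parent panel.
- Note beside the follow-up rows that they describe participants who did not enter the extension.

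**Cost.** One footnote sentence, one table entry, the aligning edits and a few lines in the SAP and table shells. There is no extra visit and, on Table 5's panel assignment, no extra scheduled blood draw. At most, local laboratories that do not already report reticulocytes with the hematology panel add that assay.
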